14.1. Information of Communities

The PNLTHA (National HAT Control Programme) in the DRC is responsible for all prevention and treatment activities regarding HAT within the country, and in particular for the supervision and coordination of the mobile teams in charge of HAT screening activities. PNLTHA is fully involved in the design and implementation of the study on fexinidazole in the DRC.

Information of the communities participating in the study will be provided at three different levels.

Firstly, the study will be presented to the public health representatives of the provinces concerned, namely the Provincial Medical Inspectors (*Médecins Inspecteurs Provinciaux*) and District Medical Officers (*Médecins Chefs de Zones*), as well as the District Administrators prior to any study-related activity in their respective geographic areas of responsibility. Information on the study will be provided by the Provincial Coordinators of the PNLTHA (*Médecins Coordinateurs*), if possible in conjunction with a DNDi representative. The

information will be based on the study protocol summary, the patient information sheet and consent form, and a summary of the Investigator Brochure.

Secondly, and before starting screening activities for the study in a given area or health zone, an adequate, HAT-experienced person with good knowledge of the area and local culture and good communication skills, i.e. either a member of a mobile team and/or a community mobiliser, will visit the local authorities, and tribal or village chiefs a few days before arrival of the mobile team, and inform them about the study and the related activities. In agreement with the local chiefs, an additional information session for the local population may be held, possibly during the usual community information session, which routinely takes place just before the start of screening activities by mobile teams. HAT is endemic in the regions where the study is to be conducted, and therefore, individuals already have a basic knowledge of the disease. In addition, most of the community mobilisers and many mobile team members have undergone specific training in community communication and HAT and will also receive additional study-specific training. Their experience and knowledge will therefore be extremely valuable in promoting a good understanding of the study.

The following information on the study will be disseminated at the community level:

- Routine procedures for detection and diagnosis of HAT;
- Primary objective of the study, i.e. to develop a safe oral drug to treat HAT that will be made available to the local population;
- Information on the new drug, the reference treatment as an alternative outside the study, the availability of a rescue treatment and on concomitant treatments as needed;
- Information on the duration of hospitalisation, number of follow-up visits up to 18 months as compared to routine treatment, importance of attending follow-up visits and possibility of visits by study staff at village level if the patient does not attend the follow-up visits at the centre;
- Information on provision of food to all HAT patients treated at the sites, regardless of whether or not they are included in the study;
- Information on organisation of transport and/or reimbursement of transport costs for patients included in the study;
- Importance of the freedom of each individual to accept or to refuse to take part in the study, after full explanation of the study. Availability of treatment in either case;
- Need for minors and patients with impaired cognitive capacities to come to the centre accompanied by a legal guardian/representative.

The third level of information concerns the individual consent of each patient (see Section 14.2. Informed Consent Process; p 73).

At the end of the study, the community will receive information on the results using the same means of communication, i.e. community mobilisers.

14.2. Informed Consent Process

14.2.1. Collection of Informed Consent from the Child's Parent/Legal Representative

Consent must be obtained from a legal representative, who can be one of the parents or any other culturally acceptable representative of the child. The mobile teams that recruit patients in the field will request that the child be accompanied by a legal representative during visits to the investigational centre.

If both parents accompany the child, consent will be obtained from both parents, however, due to logistical constraints, if only one parent accompanies the child, consent from only one parent will be considered to be acceptable.

It is the responsibility of the Investigator to obtain voluntary written informed consent from the legal representative, after adequate presentation of aims, methods, anticipated benefits, and potential hazards of the study. This task may be performed by a designee, referred to below as "facilitator", which may be a study nurse.

The written informed consent document will be translated into the local language or a language understood by the patients, and submitted to the IEC in each country for approval.

The facilitator will be chosen within the team for her/his good knowledge of the patients' preferred local language, and for his/her skills in interacting with patients. More than one facilitator may be chosen in each centre to cover all local languages and dialects.

Visual aids, including photographs, drawings and samples, will also be made available to the facilitator, describing the activities performed during the study, i.e. lumbar puncture, finger pricks, ECG, etc., and will be submitted to the IEC for approval.

The patient and his/her legal representative will be invited to attend the information session alone or together with family or friends if s/he wishes. The session will be held in a separate room in order to ensure patient confidentiality, with only one facilitator present.

The patient and his/her legal representative will first be informed about the disease, i.e. HAT, with a clear description of the signs and symptoms.

The information provided during the session will address the following topics:

- currently available treatments;
- study objective and need for scientific evaluation of a new drug;
- information on fexinidazole from previous studies (efficacy, safety...);
- number of patients to be enrolled and the duration of the study;
- criteria to fulfil to be eligible for inclusion in the study;
- patient's commitments during the study, i.e. time, compliance with study-specific procedures and attendance at follow-up visits;
- samples to be collected for laboratory tests and purpose of tests;
- benefits and risks associated with study participation;
- compensation for travel costs and provision of food during hospitalisation;
- patients' rights regarding withdrawal, rescue treatment, additional information, etc.

If the patient's legal representative wishes, s/he will be given time to discuss the information received with members of his/her community or family before giving consent. If s/he decides to agree to participate in the study, the patient's legal representative will give written consent after the information session (or later) by signing the form, provided the facilitator is convinced that the legal representative has fully understood what was explained.

Assent will be obtained from the child (see Section 14.2.3 Collection of Assent from Child; p 75).

The informed consent forms have been translated into the following local/national languages/lingua franca spoken in the areas where the study is being conducted: Lingala, Kituba/Kikongo and Tshiluba. If the patient does not speak any of the national/local languages/lingua franca and if pre-specified and authorised staff with knowledge of the dialect/local language are present, an *ad hoc* oral translation may be acceptable. The oral translation will be supported by the use of the available visual aids. The document signed by the patient will be the form in the lingua franca of his/her country/region. The procedures for illiterate patients should apply. The oral translation should be documented on the signed consent form, i.e. the person who did the translation will indicate her/his name and the language/dialect used, and will sign the form.

14.2.2. Impartial Witness

The presence of an impartial witness is mandatory if the patient's legal representative is illiterate and to collect assent from the child.

If the patient's legal representative is unable to write, his/her signature can be replaced by a fingerprint and an impartial witness should be present throughout the process of collecting consent from the legal representative.

The witness should have no connection with the research team, and, whenever possible, should be chosen by the patient's legal representative. The witness must be literate, i.e. able to read. If the patient's legal representative does not know any appropriate witness, the team will propose someone from the hospital staff who is not working in the HAT clinical unit, or any literate person from the neighbourhood who is willing to act as a witness. The study team will take all necessary measures to prepare a list of possible witnesses before the start of the study and keep this list updated, in order to find a witness quickly, whenever necessary.

The witness will sign the consent form to attest to the completeness of the information given to the patient's legal representative, and its compliance with the written information in the patient information sheet. The witness must be present throughout the entire information session.

The witness will confirm that the patient's legal representative has freely given informed consent for the child to participate in the study.

14.2.3. Collection of Assent from Child

No specific documentation or form will be used to collect assent from children enrolled in the study. Preference will be given to oral explanation in order to adapt the information to the child's level of understanding. Assent is difficult to obtain from children before 14 years of age since they do not clearly understand what benefits and risks entail (62). It is, however, easier for a child to refuse to participate than to accept to comply with a protocol. Refusal may be expressed when the protocol is explained to the child, or it may arise at any time during the course of the study. Indeed, the child is free to refuse, at any time, to undergo any invasive procedure planned in the protocol, even if s/he had initially agreed to participate in the study (62, 63). The child will be informed of this at the start of the study and at other appropriate moments. If the child refuses to undergo an invasive procedure, this will not jeopardise his/her overall participation in the study, provided that treatment compliance is acceptable.

Refusal to give assent will prevail over any other decision on the child's participation in the study.

14.2.4. Changes in the Benefit-to-Risk Assessment during the Study

If new safety information results in significant changes in the benefit-to-risk ratio, the information sheet and consent form intended for the patient's legal

representative will be reviewed and updated. The legal representative of patients currently being treated will be informed of the new information, given a copy of the revised patient information and asked to renew their consent for the child to participate in the study.

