6.1. Timing of Assessments

The timing of assessments is summarised in Table 3 (p 95).

- D-15 to D-1: Patient screening with detection of *T.b. gambiense*, pre-treatment of concomitant helminthiasis and/or malaria, if any, and ECG.
- D-4 to D-1: Baseline assessment, laboratory screening.
- D1 to D10: treatment period.
- D10 to D12: sampling for PK analyses.
- D11: EOT visit.
- D13 to D18: EOH visit; if the end of hospitalisation is extended beyond D18, the EOH visit should be performed on D18 and an additional unscheduled visit should be performed at hospital discharge.
- Additional follow-up visit: at 9 weeks after D1, i.e. D64 to D70, for patients who reach this visit starting in mid-December 2014.
- Follow-up visits: at M3, M6, M12 and M18 see Table 2 Theoretical Schedule of Visits and Acceptable Leeway). The timing of these follow-up visits is calculated from D11 (EOT).

Theoretical schedule of visits	Ideal timing of visits	Acceptable leeway*	
EOT visit	D11 after the Start of Treatment (SOT)	Between D11 and D12 after SOT	
	(D1 after EOT)	(D1 or D2 after EOT)	
EOH visit	Between D13 and D18 after SOT (D3 and D8 after EOT)	D18 at the latest	
Week 9 after D1	D64 to D70		
3 months	3 months ± 1 week after EOT	2-4 months after EOT	
6 months	6 months ± 2 weeks after EOT	5-9 months after EOT	
12 months	12 months ± 4 weeks after EOT	10-16 months after EOT	
18 months	18 months ± 4 weeks after EOT	17-21 months after EOT	

Table 2 - Theoretical Schedule of Visits and Acceptable Leeway

* The acceptable leeway for the visits starts on the first day of the period mentioned and ends on the last day of the period mentioned.

For the purposes of the study, patients will be hospitalised from their arrival at the hospital/investigational centre until D18. They will be permitted to leave hospital from D11 onwards, if their clinical status allows it.

Any additional unscheduled visits that may take place must be recorded in the CRF.

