6.3.3. Laboratory Tests

A repeat urine pregnancy test will be performed at discharge, i.e. between D13 and D18 in girls \geq 12 years of age.

Blood biochemistry and haematology assessments will be repeated on D5, D8 and D11 (EOT visit). Safety biochemistry and haematology assessments will be performed 9 weeks after intake of the first dose on D1, only in patients who reach this visit from mid-December 2014 onwards. Safety haematology and biochemistry assessments will also be performed at the 6 month follow-up visit, only in patients who reach this visit from January or February 2016 onwards. Blood samples will be analysed in the laboratory in each centre using standard equipment specifically provided for the study by the Sponsor. Whenever possible, the samples should be collected from patients in the fasting state.

Parasitology testing requires 5 mL of whole venous blood or 4 mL of CSF. The blood sample should be analysed on an mAECT column within 30 minutes after collection. The CSF sample should be examined after MSC within 15 minutes after collection. The WBC in the CSF sample should be performed within 15 minutes after collection. It is necessary to collect 5 mL of CSF to perform the two tests.

Full haematological and biochemistry analyses require at least 0.5 mL of capillary or venous blood. Capillary blood collection considerably reduces the total quantity of blood collected as compared to classical techniques. However, because it is not always feasible, collection of venous blood is permitted. For each sample, 2 mL per tube should be collected, one tube containing EDTA for haematology and one tube containing heparin lithium for biochemistry.

The urine analyses performed at the baseline assessment and at the EOT visit, (as well as the pregnancy test on D-1, on D18 and at 3 months in women), require only a few millilitres (5-10 mL) If any abnormalities are found, additional urine analyses will be requested for further investigation and to determine whether or not the abnormality constitutes an AE.

During hospitalisation, additional safety assessments such as haematology, biochemistry or urine tests may be performed at the discretion of the Investigator in order to monitor for abnormalities.

The volume and the number of samples required for each patient are presented by visit in Appendix 3 – Laboratory Assessments (p 90).

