6.5.9. Follow-up on Adverse Events

All AEs must be followed until resolution, or until the Investigator considers them to be "chronic" or "stable", or until the patient's participation in the study ends, i.e. until the final report is completed for the study in which the patient was participating.

If the AE is a laboratory abnormality with a toxicity grade \geq 3, the test must be repeated 2 to 4 days later, and then at regular intervals until the parameter reaches toxicity grade \leq 1, or until it returns to the baseline level (see Baseline Assessment).

In addition, all SAEs and all events that the Investigator (and the Coordinating Investigator or the monitor, as needed) considers as possibly related to the IP must continue to be followed even after the end of the patient's participation in the study. Such events should be followed until their resolution, or until the Investigator considers them as "chronic" or "stable." The resolution of such events must be documented in the CRF, and if they are SAEs, on an SAE follow-up form.

7. Study Duration

The enrolment period is expected to last up to 22 or 24 months. The treatment period will last 10 days.

Each patient's participation will last approximately 19 months and will include:

- pre-treatment period (pre-screening and screening, treatment of concurrent disease)
- treatment period of 10 days
- hospitalisation for 3 to 8 days after treatment
- out-patient follow-up for 12 months
- additional follow-up until 18 months.

The total duration of the study is expected to be 36 months.

8. Withdrawal Criteria

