10.1. Data and Safety Monitoring Board

A Data and Safety Monitoring Board (DSMB) consisting of at least 3 members independent from the Investigators and Sponsor, will be set up prior to study initiation. The DSMB will monitor the study in order to ensure that any harm to the patients included in the study is minimized. The DSMB will review safety data at pre-determined intervals, review all information related to the occurrence of SAEs and AEs leading to treatment discontinuation, and issue recommendations about the study if the current benefit-to-risk ratio for patients in the study seems to be unfavourable. The data and intervals will be agreed prior to, or soon after, study initiation and documented in the DSMB Charter.

The organisation of the DSMB and its operating methods will be described in the DSMB Charter, which will have been prepared and approved at the first meeting.

The DSMB of the pivotal study, DNDiFEX004, will also be in charge of studies DNDiHATFEX005 and DNDiHATFEX006.

Additional *ad hoc* members may be invited to join the DSMB if any safety concerns emerge, in order to give additional support to the competencies already present.

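### Section 14.2.4 requires new benefit-to-risk information and renewed consent only for children on treatment (10 days), leaving the 18-month follow-up outside the rule

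*Protocol*

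**What the plan says.** Section 14.2.4 of the protocol applies when new safety information significantly changes the benefit-to-risk ratio. The information sheet and consent form are then revised. The people to be told are identified in one phrase: "The legal representative of patients currently being treated will be informed of the new information". They also receive the revised information and are "asked to renew their consent for the child to participate in the study".

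The protocol fixes elsewhere what treatment means. Section 6.1 (Timing of Assessments) lists "D1 to D10: treatment period", and Section 7 (Study Duration) says "The treatment period will last 10 days". Section 7 lists follow-up separately from treatment and gives the overall length: "Each patient's participation will last approximately 19 months and will include" pre-treatment, treatment, hospitalisation and follow-up to 18 months. Section 5.3 places the end of participation at the last planned visit, month 18.

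**The concern.** The rule names a group defined by a 10-day window, although the consent it asks to renew covers the whole study. Children past Day 10 are still participants. Section 6.4.3 schedules CSF sampling at months 6, 12 and 18, and Section 6.5.4 collects serious adverse events until the end of follow-up. The primary endpoint is itself read at 12 months.

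Their families also still have choices to make. A representative may withdraw consent (Section 8.3), and a child may refuse any invasive procedure at any time (Section 14.2.3). Those rights are best exercised with current information. A site that follows Section 14.2.4 as written could give revised information to the family of a child on Day 9 and owe nothing to the family of a child on Day 12, although both remain in the same study under the same consent.

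A secondary point is that the section heading speaks of benefit and risk, while only safety information triggers action. The adult pivotal study of the same drug runs concurrently and will yield relapse data, which could change the benefit side.

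**Working it through.** **1. Is there another rule that covers follow-up?**
- Section 14.2.1 lists additional information among the patient rights explained at the initial consent session. It places no later duty on the site.
- Section 12 sends amendments to the ethics committee and, if required, the regulators. It does not mention families.
- Section 10.1 has the DSMB "issue recommendations about the study if the current benefit-to-risk ratio for patients in the study seems to be unfavourable". That covers everyone in the study, but it concerns recommendations about the study, not informing families.

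No section requires families of children in follow-up to be informed or re-consented.

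**2. The protocol's own duration.** Inputs are screening of 1 to 15 days (Section 6.1), 10 treatment days, and follow-up to 18 months after end of treatment. One month is taken as 30.4375 days.
- 18 × 30.4375 = 547.9 days.
- Shortest total: 1 + 10 + 547.9 = 558.9 days = 18.4 months.
- Longest total: 15 + 10 + 547.9 = 572.9 days = 18.8 months.

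This agrees with the stated figure of about 19 months.

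**3. Share of participation outside treatment** = 1 − (treatment days ÷ total days).

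| Basis | Calculation | Outside |
|---|---|---|
| First dose to month 18 | 1 − 10/557.9 | 98.2% |
| Stated 19 months (578.3 days) | 1 − 10/578.3 | 98.3% |
| Last visit at month 17 (Table 2 leeway) | 1 − 10/527.4 | 98.1% |
| Last visit at month 21 (Table 2 leeway) | 1 − 10/649.2 | 98.5% |
| One make-up day (Section 8.1) | 1 − 11/558.9 | 98.0% |
| Hospital stay to Day 18, visit at month 18 | 1 − 18/557.9 | 96.8% |

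With the hospital-stay reading, the visit leeway and up to 15 screening days, the range is 96.6% to 97.3%.

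**4. Share of children on a given date.** This needs an accrual assumption. Take even enrolment of 125 children over 22 to 24 months.
- On treatment at any time: 125 × 10/(24 × 30.4375) = 1.7 children, or 1.9 with 22 months.
- Up to month 18 of enrolment, the share of dosed children past treatment is 1 − 10/(30.4375 × t), where t is months since the first dose. The sample size and the accrual period cancel.
- t = 3: 89.0%. t = 6: 94.5%. t = 12: 97.3%. t = 18: 98.2%.
- From month 18 to the end of enrolment it stays at about 98.2%. After the last child's final dose it is 100%, and that child still has 18 months of follow-up.

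**The case against.** The strongest reply is that the phrase is loose drafting. The section heading refers to changes during the study, and the same sentence asks for consent "asked to renew their consent for the child to participate in the study", which runs to month 18. Sites may well read it as all enrolled patients. That is plausible, but the protocol uses treatment period consistently for Days 1 to 10 and refers to patients in the study when it means everyone, as in Section 10.1. The looser reading is a reason to correct the words, since it suggests the authors would accept the correction.

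Stronger conclusions are tempting, and the documents do not support them:

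- *Families in follow-up would be kept uninformed.* The protocol does not bar informing them. It only sets no requirement to do so.
- *These families cannot react to a problem.* Sections 6.4.4 and 6.5 tell patients to return at any time if unwell or if they have an adverse event. Relapse is tested at scheduled visits, consent may be withdrawn, and the child may refuse procedures and is reminded of this at appropriate moments. What may be missing is the new information, not the means to act.
- *The safety blood tests added mid-study show the gap in operation.* Week-9 tests apply "for patients who reach this visit starting in mid-December 2014" and month-6 tests "only in patients who reach this visit from January or February 2016 onwards". Nothing says that either followed from a significant change in benefit-to-risk, which is the only trigger of Section 14.2.4, and nothing says whether families were re-consented. Such changes also need ethics approval under Section 12.
- *The safety-only trigger is an error.* Each child's own relapse is already tested on schedule, so adding efficacy information is a drafting improvement.

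**Conclusion.** The point holds as a defect in a patient-protection rule. As written, the duty to inform and re-consent covers a 10-day window within about 19 months of participation. About 98% of each child's participation time falls outside it (98.0% to 98.5% across the visit windows and one make-up day), or about 97% if being treated is taken as the hospital stay to Day 18. These shares rest only on the protocol's own durations.

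A reader might infer that 98% of the children in the study are uncovered at any time. That holds only from about month 18 of enrolment, and only under the assumed even accrual. The share is lower earlier and reaches 100% once dosing has ended, whatever the accrual pattern.

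This is a matter of consent wording. It does not touch the sample size, the type I error or the power, and the documents do not show that consent for the primary-endpoint follow-up was in fact compromised.

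**What to change.** In Section 14.2.4, replace the group named in the re-consent sentence with *all patients still in the study, on treatment or in follow-up to 18 months*. State that information and renewed consent are obtained at the next scheduled visit or earlier, and that the child's assent is sought again at the same time. The words *or earlier* matter, because scheduled visits after month 6 are six months apart. Optionally, widen the trigger to *new safety or efficacy information*.

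The cost is an amendment with ethics approval under Section 12 and some extra consent work. Much of that work can use the existing visits at months 3, 6, 12 and 18. A few families may withdraw once informed. A withdrawal before month 12 that leaves the 12-month outcome missing would count as a failure under the primary imputation in Section 9.2, where the success rule of 109 out of 125 allows 125 − 109 = 16 failures. That is a reason to record withdrawals and their reasons carefully, not a reason to leave families out of the rule.
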